11.12.2 LCTC Responsibilities

The trial Sponsor, Alder Hey Children’s NHS Foundation Trust have delegated to LCTC the duty of onward reporting of safety events to REC, MHRA and Sponsor.

Safety events which are assessed as “serious”, “related” and “unexpected”, will be classed as SUSARs and will be onward reported in an expedited manner to MHRA and REC within the following timeframes:

- SUSARs which are fatal or life-threatening – **as soon as possible and in any case no later than 7 days** of receipt at the LCTC. If the initial report is incomplete, a complete report will be submitted within an additional 8 days.
- SUSARs that are not fatal or life-threatening – **within 15 days** of receipt at the LCTC

Additionally, SUSARs will be reported to the trial Sponsor within agreed timelines.

The PIs at all institutions participating in the trial will be notified of any SUSARs within a reasonable timeline as per LCTC Safety Processing Plan.

The LCTC will submit annual reports containing safety information to REC and MHRA.

Information on safety events will also be reported to TSC/IDSMC. Inconsistencies regarding safety reporting noted at a given site may prompt additional training at sites, with the potential for the LCTC to carry out site visits if there is suspicion of unreported safety events in patient case notes. Additional training will also be provided if there are unacceptable delays in safety reporting timelines.

11.13 Urgent Safety Measures (USMs)

An USM is a procedure to protect clinical trial participants from any immediate hazard to their health and safety but has not previously been defined by the protocol. It can be put in place prior to authorisation by the REC and the MHRA via the usual amendment process.

The LCTC will notify the REC and MHRA immediately and, in any event, within 3 days that such a measure has been taken and the reasons why it has been taken. The initial notification to the REC and MHRA will be by telephone (ideally within 24 hours) and a notice in writing will be sent within 3 days, setting out the reasons for the USM and the plan for further action. After discussion with the REC and MHRA, further action will be agreed, which may include submission of a temporary halt, or permanent termination of the trial.

Following notification of a USM, a substantial amendment should be submitted as soon as possible to the REC and ideally within two weeks to the MHRA. If the trial is temporarily halted it may not recommence until authorised to do so by the REC and MHRA. If the trial is halted or permanently terminated before the date specified for its conclusion (in the original applications to REC and MHRA), LCTC will notify the REC and MHRA within 15 days of the date of halt/termination.

11.14 Contact Details and Out-of-hours Medical Cover

As this trial is low risk and the IMP and comparator are given in standard NHS practice and have a well-established safety profile emergency, out-of-hours medical care will be in line with usual NHS arrangements and local standard practice; no special provision is required for participants. All participants will be provided with a contact card and copy of the information sheet which includes information about their participation and contact details for the local research team who may be contacted if necessary. During office hours, the CI or delegate are able to provide medical advice in relation to participation using the contact details listed at the beginning of this document.

12 STATISTICAL CONSIDERATIONS

12.1 Sample Size

12.1.1 Sample Size Calculation

The sample size calculation is based on the recommendations by Borm [32]. The method by Borm uses a two-step approach, firstly calculating the required sample size as if a t-test were to be used then the number of patients is multiplied by a 'design factor' to give the number of patients required for the analysis using ANCOVA.

Based on data from the HTA feasibility study [7], the mean change from baseline to six weeks in cJADAS10 in those patients who had oral corticosteroids was -6.37 with SD 5.05 and the correlation between baseline and six weeks was 0.55.

Applying the first step, a sample size of 87 in each group (174 patients in total) is required to have 90% power to detect a difference in means of 2.5 (which equates to an effect size of 0.50), assuming that the common within group SD is 5.05, using a two group t-test with a 5% two-sided significance level. Assuming 5% missing data the total required sample size would be 184.

Stage 2 applies the design factor (which is equal to 0.6975 (1-0.55²)) to the sample size obtained in Stage 1, which then gives a total number of required patients to be 130.

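### Section 12.1.1 applies the ANCOVA factor 1-ρ² to a sample size built on the SD of change, so 90% power at 130 patients does not follow from the stated inputs

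*Protocol*

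**What the plan says.** Protocol section 12.1.1 takes its planning values from the feasibility study. It reports that "the mean change from baseline to six weeks in cJADAS10 in those patients who had oral corticosteroids was -6.37 with SD 5.05", and that "the correlation between baseline and six weeks was 0.55". Stage 1 is a two-group t-test with 90% power at the two-sided 5% level for a difference of 2.5, "assuming that the common within group SD is 5.05". This gives 87 per group, 174 in total, and 184 after allowing for 5% missing data. Then "Stage 2 applies the design factor (which is equal to 0.6975 (1-0.55²)) to the sample size obtained in Stage 1", giving a total of 130.

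Section 12.4 makes the primary analysis an ANCOVA adjusted for baseline and the stratification factor. Section 6.2 defines the primary outcome as the change in JADAS10 between weeks 0 and 6. No section gives the SD of the score at baseline or at week 6.

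**The concern.** The two-step method is sound if the SD in the first step and the correlation in the second describe the same outcome. The factor 1-ρ², with ρ the correlation between baseline and week 6, converts a t-test on the week-6 score into an ANCOVA. The protocol's t-test instead uses the SD of the change. That SD already depends on ρ and on both visits' SDs, so the gain from adjusting for baseline needs a different factor.

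At stake is the stated power of the primary analysis. The total of 130 is the trial's headline size, and a null result would be read against a 90% power that the written calculation does not support.

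**Working it through.** **Inputs (all from Protocol 12.1.1):** difference 2.5; SD of change 5.05; ρ = 0.55 between baseline and week 6; two-sided 5%; 90% power; 5% missing.

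**Reproducing the protocol's figure.** A two-group t-test (non-central t) with difference 2.5 and SD 5.05 needs 87 per group, so 174. Then 174 / 0.95 = 183.2, rounded up to 184. The factor is 1 - 0.55² = 0.6975, and 184 × 0.6975 = 128.3, which is 129, or 130 for equal arms. Every stated step reproduces.

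**Which factor matches which SD.** Write SD0 and SD6 for the SDs at baseline and week 6, and k = SD0/SD6.

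- ANCOVA residual variance = SD6² × (1 - ρ²).
- Variance of change = SD0² + SD6² - 2ρ·SD0·SD6 = SD6² × (k² + 1 - 2ρk).
- Factor to apply to a change-score t-test size = (1 - ρ²) / (k² + 1 - 2ρk). This equals 1 minus the squared correlation of baseline with change.

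At k = 1 the factor is 0.6975 / 0.90 = 0.775, which is (1+ρ)/2. The denominator equals 1, and the protocol's 0.6975 becomes correct, when k² = 2ρk, that is k = 2ρ = 1.1. The week-6 SD is then itself 5.05.

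**Effect on N and power.** Residual SD = 5.05 × √factor. N needed = 184 × factor, rounded up to equal arms. Power is for 130 randomised with 5% missing (123.5 analysed, 61.75 per arm), from the non-central t with non-centrality 2.5 / (residual SD × √(2/61.75)). The SD ratio is an assumption, so a range is shown.

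| SD0/SD6 | Factor | Residual SD | 184 × factor | N needed | Power of 130 |
|---|---|---|---|---|---|
| 0.9 | 0.8506 | 4.658 | 156.5 | 158 | 84.1% |
| 1.0 | 0.7750 | 4.446 | 142.6 | 144 | 87.3% |
| 1.1 | 0.6975 | 4.218 | 128.3 | 130 | 90.4% |
| 1.2 | 0.6228 | 3.985 | 114.6 | 116 | 93.3% |

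At equal SDs with no missing data, 130 patients give 88.9%.

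**The case against.** The strongest reply is that no loss of power has been shown. The documents give neither visit's SD. At a ratio of 1.1 the protocol's 130 is reproduced exactly, and at 1.2 it is more than enough. A reader might infer that the correlation has been counted twice and that the trial is therefore underpowered. The documents do not support that: the shortfall appears only for ratios below 1.1, and equal SDs is a convenient assumption, not a figure from the protocol.

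Two further points also stand. The effect is modest near equal SDs: the residual SD moves from 4.218 to 4.446, about 5%, no more than ordinary uncertainty in a planning SD. That SD is in any case a cJADAS10 value from patients on oral corticosteroids, used for a trial whose outcome is JADAS10. And the ANCOVA, its estimate and its confidence interval are unaffected.

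Three possible defences do not stand:

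- **The outcome is a change score.** With baseline as a covariate, ANCOVA gives the same treatment effect and residual variance whether change or the week-6 score is the response, so this does not make 1-ρ² the right factor for a change SD.
- **5.05 may also be the week-6 SD.** The text labels it as the SD of the change.
- **0.55 may be the correlation of baseline with change.** The text describes it as the correlation between baseline and six weeks.

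**Conclusion.** The SD and the design factor in section 12.1.1 do not match, and 90% power at 130 does not follow from the inputs given. It holds only under an unstated baseline/week-6 SD ratio of 1.1. Below that ratio 130 is too few for 90% power; above it, more than enough. Over ratios from 0.9 to 1.2 the power of 130 runs from about 84% to 93%, and at equal SDs it is about 87%, or some 14 patients short (144 against 130).

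These figures rest on the protocol's change SD, correlation and 5% missing data, and make no allowance for the site terms in the model. The defect is a mismatched input, not an arithmetical slip, and its direction cannot be settled from the protocol. It should be fixed, as a correction to the justification of the sample size; it is not evidence that the design fails.

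**What to change.** Rewrite section 12.1.1 on one consistent basis, using the feasibility data that the protocol already cites:

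- take the SD of the week-6 score and apply 1-ρ² with ρ = 0.55; or
- keep the change SD of 5.05 and apply 1 minus the squared correlation of baseline with change. This equals (1+ρ)/2 = 0.775 only if the two visits' SDs are equal, so 0.775 should not be used without saying so.

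In either case, write down the SD assumption, keep N = 130 and restate the power it gives: about 87% if equal SDs are assumed, otherwise whatever the feasibility SDs yield.

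The cost is a rewording of one section and possibly a slightly less favourable stated power. No extra patients are needed, and the primary analysis does not change.

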12.2 Method of Randomisation

12.2.1 Allocation Sequence Generation

Participants/legal guardians who give their informed consent for the randomised controlled trial will complete baseline processes and outcome measures before being individually randomised. The randomisation will be performed by the site team using 24-hour web-based randomisation system to protect against subversion whilst ensuring that the trial maintains good balance to the allocation ratio of 1:1 both within each stratum and across the trial. This system will be set up, maintained and monitored independently of the trial statistician or other trial staff.

12.2.2 Concealment and Implementation of Allocation Sequence

Patient allocations will be irrevocably generated upon completion of the web-based randomisation form by a delegated member of the trial research team. Allocation concealment will be ensured as the service will not release the randomisation code until the patient has been recruited into the trial; this takes place after all baseline measurements have been completed.

12.3 Interim Analyses

There are no planned interim analyses for this trial.

Analyses of the accumulating data will be performed at regular intervals (at least annually) for review by an IDSMC. These analyses will be performed at the LCTC. The IDSMC will be asked to give recommendations to the TSC on whether the accumulated data from the trial, together with results from other relevant trials, justifies continuing recruitment of further patients or further follow-up. A decision to discontinue recruitment, in all patients or in selected subgroups will be made only if the result is likely to convince a broad range of clinicians including participants in the trial and the general clinical community.

12.4 Analysis Plan

A full statistical analysis plan (SAP) will be written prior to the conduct of any comparative analysis of the treatment arms. The main features of the SAP are summarised below:

Analyses will be by 'intention to treat' for the primary and secondary outcomes on all randomised participants, in the group to which they were allocated, and for whom the outcomes of interest have been observed or measured.

Demographic and baseline characteristics will be summarised separately using descriptive statistics for each randomised group to allow assessment of whether balance was achieved between randomised groups. This will include sex, age, ethnicity, JIA subtype (ILAR classification) and other relevant characteristics. No statistical testing of demographic and baseline differences between groups will be performed.

Primary and secondary outcomes at 0 weeks (baseline), 6 weeks, 12 weeks, 24 weeks and 52 weeks will be summarised for each treatment group using descriptive statistics at each time point.

If normally distributed the primary analyses will report the difference between group means (with 95% confidence intervals) using an analysis of covariance (ANCOVA), adjusting for baseline and the stratification factor (recommended by ICH E9), this will permit greater power to detect the minimum important difference than the t- test.

Binary outcomes will be reported using relative risks and 95% confidence intervals. Continuous outcomes will be reported using a linear mixed effects method including all patients, all time-points and adjusting for the stratification factor. Time to event outcomes will be summarised by Kaplan-Meier curves and compared overall using log-rank tests and survival regression methods.

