7 TRIAL DESIGN

This trial is designed as a multi-centre, open-label randomised controlled trial with 1:1 allocation ratio, stratified by site.

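### The mixed model for continuous outcomes names site but not baseline as an adjustment and takes in week 0, so it may lose precision that the primary ANCOVA keeps

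*Protocol*

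**What the plan says.** Protocol section 12.4 gives each model its own adjustment set. The primary comparison is made "using an analysis of covariance (ANCOVA), adjusting for baseline and the stratification factor (recommended by ICH E9"), and the protocol justifies this by the extra power over a t-test. The general rule for continuous outcomes follows in the next paragraph: "Continuous outcomes will be reported using a linear mixed effects method including all patients, all time-points and adjusting for the stratification factor". Baseline appears in the first statement and not in the second.

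Week 0 counts as an outcome time in this plan. Section 12.4 says "Primary and secondary outcomes at 0 weeks (baseline), 6 weeks, 12 weeks, 24 weeks and 52 weeks will be summarised for each treatment group", and the table in section 6.2 gives weeks 0, 6, 12, 24 and 52 for JADAS 10/27/71, pain VAS, CHAQ and CHU-9D. The stratification factor is site (section 7: "open-label randomised controlled trial with 1:1 allocation ratio, stratified by site").

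The protocol does not say whether week 0 is a response or a covariate in the mixed model, whether the arms share a week-0 mean, whether there is a treatment-by-visit term, or which contrast is reported.

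**The concern.** Randomisation follows the baseline measurements (section 12.2.2), so the true treatment difference at week 0 is zero. A model that estimates a separate week-0 mean for each arm spends information on a quantity already known. Depending on the contrast reported, it then either subtracts a noisy baseline difference or ignores baseline altogether. If instead one treatment effect is fitted across all visits, the null week-0 difference is averaged into it and pulls it towards zero.

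This matters here because section 12.1.1 reduces the sample size by a design factor that is earned only when baseline is used efficiently. The secondary continuous outcomes are analysed in that same reduced sample.

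**Working it through.** **Inputs.** From section 12.1.1: SD 5.05 (change in cJADAS10), correlation ρ = 0.55 between baseline and week 6, difference 2.5, two-sided 5% level, 90% power, 5% missing data. From section 6.2: five visits. Assumed for illustration: equal SDs at baseline and follow-up, compound symmetry across visits, and 130 × 0.95 = 123.5 evaluable patients, or 61.75 per arm.

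**The plan's own figure.** A two-group t-test with SD 5.05 and difference 2.5 needs 87 per group, or 174. Allowing for 5% missing data, 174 / 0.95 = 183.2, so 184. The design factor is 1 − 0.55² = 0.6975, and 184 × 0.6975 = 128.34, which is 129, or 130 as an even total. The stated 130 is reproduced.

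**Variance factors relative to the single-visit variance**
- Baseline as covariate: 1 − ρ² = 0.6975.
- Change contrast with free arm means at week 0: 2(1 − ρ) = 0.90.
- Follow-up-value contrast with free arm means at week 0: 1.00.

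Variance ratios to the baseline-adjusted analysis are 0.90 / 0.6975 = 1.29 and 1 / 0.6975 = 1.43. SE ratios are √1.29 = 1.14 and √1.43 = 1.20.

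**In the plan's units**, SE = 5.05 × √(factor × 2 / 61.75), with power for a difference of 2.5:

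| Specification | SE | Power |
|---|---|---|
| Baseline as covariate | 0.759 | 91% |
| Week 0 as response, common arm mean | 0.759 | 91% |
| Week 0 as response, free arm means, change contrast | 0.862 | 83% |
| Week 0 as response, free arm means, week-6 contrast | 0.909 | 79% |

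An exact generalised-least-squares calculation for the five-visit model gives the same SEs in SD units: 0.150 with a common week-0 mean (identical to ANCOVA), 0.171 for the change contrast and 0.180 for the week-6 contrast.

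The table follows section 12.1.1 in using 5.05 as the SD to which the design factor applies. If 5.05 is read strictly as the SD of change, the single-visit SD is 5.05 / √0.90 = 5.32 and the powers become 88%, 79% and 74%. The SE ratios do not change.

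**Range of ρ**, since 0.55 is given for one score at one visit:

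| ρ | Excess SE, change contrast: √(2(1 − ρ) / (1 − ρ²)) − 1 | Excess SE, follow-up value: 1 / √(1 − ρ²) − 1 |
|---|---|---|
| 0.2 | 29% | 2% |
| 0.4 | 20% | 9% |
| 0.55 | 14% | 20% |
| 0.7 | 8% | 40% |

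**Pooled effect.** With a true effect of 0 at week 0 and a constant effect at the other four visits, a single treatment main effect estimates (0 + 1 + 1 + 1 + 1) / 5 = 0.80 of the constant effect.

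**The case against.** The strongest reply is that section 12.4 is only an outline ("The main features of the SAP are summarised below") and that covariate coding is normally left to the SAP. That would settle the matter if the section were silent. It is not: it names an adjustment set for each model, and a SAP that followed the mixed-model sentence literally would adjust for site alone.

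A second reply carries more weight. If week 0 is a response, baseline is already in the model, and with a common week-0 mean the precision equals that of ANCOVA. This stands. A reader might infer that every secondary continuous estimate will be less precise; the documents do not support that, because the loss depends on a specification they leave open. Likewise the 80% dilution needs a single pooled effect, which the protocol does not state.

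A reader might also infer that the binary and time-to-event analyses ignore the randomisation stratum. The text ("Binary outcomes will be reported using relative risks and 95% confidence intervals"; "Time to event outcomes will be summarised by Kaplan-Meier curves and compared overall using log-rank tests and survival regression methods") neither includes nor excludes site, and section 6.2 labels no outcome as time-to-event. The gain would also be doubtful. With 130 patients over at least 14 sites, there are about 9 per site (130 / 14 = 9.3). In a simulation assuming 14 sites of equal expected size and permuted blocks of four, the spread of the log relative risk was practically the same crude and site-adjusted: 0.159 and 0.159 with no site effect, 0.165 and 0.165 at site SD 0.5, and 0.153 and 0.152 at site SD 1.0. Log-rank power, unstratified against stratified, was 49% against 46%, 42% against 43%, and 28% against 44%. Stratification clearly helped only when the site effect was large.

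Finally, JADAS10 at week 6 appears under both the primary and the secondary outcomes. Two models for it are not in themselves a fault: the ANCOVA is designated primary, and a longitudinal model of the same score is an ordinary secondary analysis.

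**Conclusion.** The point holds for the mixed model of continuous outcomes, conditionally. As written, with site as the only adjustment and week 0 among the time-points, the model is less efficient than the baseline-adjusted analysis unless the week-0 arm means are constrained to be equal. At ρ = 0.55 the cost is about 14% in SE for a change contrast, equivalent to using 0.6975 / 0.90 = 78% of the patients, and about 20% for a follow-up-value contrast, equivalent to about 70%. Which figure applies depends on the contrast chosen, and its size depends on correlations not given for other outcomes and visits. The calculations also assume equal SDs and compound symmetry.

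The primary analysis and the sample size are unaffected. This is a worthwhile improvement available at no cost, not an error that undermines the trial.

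**What to change.** In section 12.4, and then in the SAP, replace the mixed-model sentence with one that says how baseline enters. Either of these will do:
- weeks 6, 12, 24 and 52 as responses, with the outcome's own baseline value, treatment, visit, treatment-by-visit and site as terms; or
- week 0 kept as a response, with the arm means constrained to be equal at that visit, and treatment-by-visit terms for the later visits plus site.

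In both cases state that the treatment difference is reported at each visit. The cost is wording only: baseline values of these outcomes are already collected, and no visit, measurement or patient is added.

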13 DATA MANAGEMENT

13.1 Source Documents

The case report form (CRF) will be considered the source document for data where the information cannot be obtained from the medical records and is recorded directly in the trial specific CRF.

The trial Source Data Checklist will document where the source data for the trial is routinely held. The investigator is required to confirm that the information held in the checklist is an accurate reflection of data collection practices at site. A copy of this checklist should be retained in the Investigator Site File

13.2 Data Collection Methods

Data are to be entered into an electronic secure web-based trial specific system by approved members of the research team at site.

The following CRFs are subject to expedited reporting and need to be returned to LCTC in paper format/secure data transfer:

- Serious Adverse Event

13.2.2 Questionnaires and Assessments

These are described in section 10.7. Participants or if appropriate, a parent/legal guardian of the participant will be given the following questionnaires and assessments to complete: CHAQ, CHU-9D, CAPTURE-JIA PROM, pain VAS, PGA-VAS, Tanner self-assessment and the Resource Use Questionnaire. These are described in section 10.7. The research team will enter data from these questionnaires and assessments onto the electronic secure web-based trial-specific system. The questionnaires and assessments will then be stored in the ISF.

